- aa. Urine sample for selected renal biomarkers including retinol binding protein and beta-2-microglobulin (other biomarkers might be measured).
- bb. For postmenopausal women only: An FSH level in the postmenopausal range may be used to confirm a postmenopausal state in women not using hormonal contraception or hormonal replacement therapy. However, in the absence of 12 months of amenorrhea, a single FSH measurement is insufficient to confirm a woman is not of childbearing potential (see Section 10.5, Appendix 5, Contraceptive and Barrier Guidance).
- cc. Additional samples may be collected for AFP testing in case of ALT flares.
- dd. Urine pregnancy tests should be done at least every 4 weeks. On days of study intervention administration (JNJ-3989 +/- nivolumab), the urine pregnancy test should be performed pre-dose.
- ee. Only applicable to participants who are enrolled at a site with access to a Fibroscan device. A Fibroscan assessment will only be done at baseline if it was not done at screening.
- ff. HBV genotype will be determined at baseline using a standard genotyping assay if HBV DNA levels are sufficiently high. Exploratory genotyping may be performed.
- gg. HBcrAg and HBV RNA samples may be batched, and only selected samples may be tested at the sponsor's request. Samples can be used for assessment of other serologic/virologic markers of HBV.
- hh. Samples may be sequenced based on the sponsor virologist's request, considering the HBV DNA levels. In case of a virologic breakthrough/flare, additional samples for viral sequencing may be taken.
- ii. Exploratory serology samples may be analyzed at the sponsor's discretion. Samples may be used to assess virologic or serologic markers of HBV.
- jj. All participants will have sparse PK samples taken 2 to 6 hours after administration of the study intervention(s). An optional sample may be taken 6 to 24 hours after administration of the study intervention(s). When both JNJ-3989 and nivolumab are administered at the same visit, the sparse PK samples will be collected 2-6 hours (mandatory samples) and 6-24 hours (optional sample) after the end of nivolumab infusion. In addition, for Arm 2, a pre-dose PK sample will be taken prior to administration of nivolumab at Weeks 20 and 24. For all samples, the date and time of the preceding 2 intakes of NA, the date and time of the previous JNJ-3989 and nivolumab administration, as applicable, and the date and time of PK sampling should be recorded. Before leaving the study site, the participant's well-being should be confirmed.
- kk. These samples are optional and will only be collected from participants who consent separately to this component of the study. The exploratory host genotyping sample should preferably be collected at baseline.
- ll. If the FNA biopsy cannot be completed on Day 1, it may be completed at a later visit without constituting a protocol deviation. A separate visit may be scheduled for FNA biopsies and blood sample collections for safety labs required prior to FNA biopsy procedures. Participants may stay overnight at the study site after the FNA biopsy procedures at the investigator's discretion. Prior to each FNA biopsy, a recent ( $\leq 2$  weeks) coagulation and hematology panel are required, to ensure normal platelet count and normal coagulation parameters.
- mm. On the days of nivolumab infusion, whole blood samples for RO assay will be taken before nivolumab infusion (pre-dose) and 2 hours +/- 10 minutes after the end of nivolumab infusion (post-dose). At the visits without nivolumab infusion, the sample will be taken at any time during the visit.

- nn. PBMC samples will be collected at selected sites only. Additional PBMC samples may be taken in case of ALT flares, upon discussion with the sponsor, and may require an unscheduled visit. If a PBMC sample has been taken within the last 4 weeks prior to the unscheduled visit, no new PBMC sample is to be collected. PBMC whole blood samples need to be collected before starting nivolumab infusion.
- oo. Adverse events and concomitant medications will be monitored from the time a signed and dated ISA ICF is obtained until completion of the participant's last ISA-related procedure.
- pp. Autoantibodies tests include antinuclear antibodies; anti-smooth muscle antibodies; anti-mitochondrial antibodies; anti-thyroid peroxidase antibodies; anti-neutrophil cytoplasmic antibodies and rheumatoid factor.

## 1.3.2. Schedule of Activities – Follow-up Phase

| Study Period   | Follow-up a,b,c,d |                |          |                |                |           |           |           |                          |
|--|------------------------------|----------------|----------|----------------|----------------|-----------|-----------|-----------|--------------------------|
|  | FU W4                        | FU W8          | FU W12   | FU W16         | FU W20         | FU W24    | FU W32    | FU W40    | FU W48 / WD e |
| Visit Week (W)   |                              |                |          |                |                |           |           |           |                          |
| Study Day (Window)   | 29 +/-4d                     | 57 +/-4d       | 85 +/-4d | 113 +/-4d      | 141 +/-4d      | 169 +/-4d | 225 +/-4d | 281 +/-4d | 337 +/-4d                |
| Study Intervention / Background Treatment                                 |                              |                |          |                |                |           |           |           |                          |
| Intake of NA c  | X                            | X              | X        | X              | X              | X         | X         | X         | X                        |
| Safety Assessments  |                              |                |          |                |                |           |           |           |                          |
| Body weight and symptom-directed physical examination                            | X                            | X              | X        | X              | X              | X         | X         | X         | X                        |
| Vital signs f   | X                            | X              | X        | X              | X              | X         | X         | X         | X                        |
| Triplicate 12-lead ECG g  | X                            |                |          |                |                |           |           |           |                          |
| Liver ultrasound h  |                              |                |          |                |                | X         |           |           | X                        |
| Medical resource utilization i  | X                            | X              | X        | X              | X              | X         | X         | X         | X                        |
| Clinical Laboratory Tests   |                              |                |          |                |                |           |           |           |                          |
| Hematology j  | X                            | X              | X        | X              | X              | X         | X         | X         | X                        |
| Blood chemistry (including cystatin C and liver function tests) k,l,m | X                            | X n | X        | X n | X n | X         | X         | X         | X                        |
| CRP  |                              |                | X        |                |                | X         |           |           | X                        |
| Blood coagulation  | X                            |                | X        |                |                | X         |           |           | X                        |
| Urinalysis o  | X p               | (X)            | (X)      | (X)            | (X)            | (X)       | (X)       | (X)       | X p           |
| Urine chemistry q   | X p               | (X)            | (X)      | (X)            | (X)            | (X)       | (X)       | (X)       | X p           |
| Autoantibodies bb   |                              |                |          |                |                | X         |           |           | X                        |
| AFP test r  |                              |                |          |                |                | X         |           |           | X                        |
| Urine pregnancy test (women of childbearing potential) s              | X                            | X              | X        | X              | X              | X         | X         | X         | X                        |
| TSH, T3, and T4  |                              | X              |          |                |                | X         |           |           | X                        |
| Efficacy Evaluations  |                              |                |          |                |                |           |           |           |                          |
| Fibroscan t   |                              |                |          |                |                | X         |           |           | X                        |
| HBV Virology  |                              |                |          |                |                |           |           |           |                          |
| Blood sampling for HBV DNA   | X                            | X              | X        | X              | X              | X         | X         | X         | X                        |
| Blood sampling for HBV RNA u  |                              |                | X        |                |                | X         |           |           | X                        |
| HBV Serology  |                              |                |          |                |                |           |           |           |                          |
| Blood sampling for:  |                              |                |          |                |                |           |           |           |                          |
| Anti-HBs and anti-HBe  |                              |                |          |                |                | X         |           |           | X                        |
| HBsAg (quantitative)   |                              | X              | X        | X              | X              | X         | X         | X         | X                        |
| HBeAg (quantitative)   |                              |                | X        |                |                | X         |           |           | X                        |
| HBcrAg u  |                              |                | X        |                |                | X         |           |           | X                        |
| Exploratory serology v  |                              |                | X        |                |                | X         |           |           | X                        |

| Study Period   | Follow-up a,b,c,d |          |          |           |           |           |           |           |                          |
|--|------------------------------|----------|----------|-----------|-----------|-----------|-----------|-----------|--------------------------|
|  | FU W4                        | FU W8    | FU W12   | FU W16    | FU W20    | FU W24    | FU W32    | FU W40    | FU W48 / WD e |
| Visit Week (W)   |                              |          |          |           |           |           |           |           |                          |
| Study Day (Window)   | 29 +/-4d                     | 57 +/-4d | 85 +/-4d | 113 +/-4d | 141 +/-4d | 169 +/-4d | 225 +/-4d | 281 +/-4d | 337 +/-4d                |
| Exploratory Host Biomarkers                             |                              |          |          |           |           |           |           |           |                          |
| Whole blood RNA gene expression                                |                              |          |          |           |           |           |           |           | X                        |
| Whole blood single-cell profiling                              |                              |          | X        |           |           |           |           |           | X                        |
| Host serum proteins  |                              |          | X        |           |           |           |           |           | X                        |
| Optional FNA collection w,x                         |                              |          |          |           |           |           |           |           | (X) cc        |
| Antidrug antibodies to JNJ-3989                                |                              |          | X        |           |           | X         |           |           | X                        |
| Antidrug antibodies to nivolumab                               |                              |          | X        |           |           | X         |           |           | X                        |
| Blood sample collection for RO assay (nivolumab): y |                              |          |          |           |           |           |           |           |                          |
| Arm 1  |                              |          | X        |           |           |           |           |           |                          |
| Arm 2  |                              |          | X        |           |           | X         |           |           |                          |
| Immune Monitoring                                       |                              |          |          |           |           |           |           |           |                          |
| Immune cells (PBMCs) (selected sites only) z        |                              | X        |          |           |           |           |           |           |                          |
| Ongoing Participant Review                              |                              |          |          |           |           |           |           |           |                          |
| Concomitant therapy aa                              | X                            | X        | X        | X         | X         | X         | X         | X         | X                        |
| Adverse events aa                                   | X                            | X        | X        | X         | X         | X         | X         | X         | X                        |

(X): optional or conditional sample; AFP: alpha-fetoprotein; ALT: alanine aminotransferase; AST: aspartate aminotransferase; CKD-EPI: Chronic Kidney Disease Epidemiology Collaboration; CRP: C-reactive protein; d: day; DAIDS: Division of Acquired Immunodeficiency Syndrome; DBP: diastolic blood pressure; DNA: deoxyribonucleic acid; ECG: electrocardiogram; eGFR: estimated glomerular filtration rate; EOSI: end of study intervention; FNA: fine needle aspiration; FU: follow-up; GI: giga; HBc: hepatitis B core protein; HBe(Ag): hepatitis B e (antigen); HBcrAg: hepatitis B core-related antigen; HBs(Ag): hepatitis B surface (antigen); HBV: hepatitis B virus; ICF: informed consent form; ISA: intervention-specific appendix; NA: nucleos(t)ide analog; PBMC: peripheral blood mononuclear cells; PK: pharmacokinetic; RNA: ribonucleic acid; RO: receptor occupancy; SBP: systolic blood pressure; T3: triiodothyronine; T4: thyroxine; TSH: thyroid-stimulating hormone; W: week; WD: withdrawal.

- a. All follow-up study visits are to be scheduled relative to the Week 24/EOSI/WD visit (see Section 1.3.1). An unscheduled visit can be performed upon the investigator’s discretion, in case of HBV DNA elevations, ALT elevations, other signs of worsening of liver disease, or for any other reason.
- b. At all visits, blood samples should be collected before intake of NA, unless indicated otherwise.
- c. Participants who discontinue study prematurely will have an early WD visit. Participants who withdraw consent will be offered an optional safety follow-up visit to occur on the day of consent withdrawal. For the optional safety follow-up visit, assessments are at the investigator’s discretion and could be similar to the early WD visit.
- d. Refer to Section 8.3.6.1 for management of intervention-emergent ALT/AST elevations.
- e. NA prescription should follow the standard of care. In between study visits, participants will take NA at home and will bring their NA with them to each study visit. At study visits, the NA should be taken on site. Compliance will be assessed by the investigator based on participant interview.
- f. Vital signs include supine SBP, DBP, pulse rate, and body temperature. Vital signs should preferably be assessed prior to any blood sampling.
- g. ECGs should be completed before any tests, procedures or other consultations for that visit. All ECGs will be read centrally.
- h. For liver ultrasound, a window of 1 week is allowed before or after the scheduled visit.
- i. The medical resource utilization data will include: number and duration of medical care encounters, duration of hospitalization, number and character of diagnostic and therapeutic tests and procedures, and outpatient medical encounters and treatments. For more details, refer to Section 8.9.
- j. The following criteria will trigger additional unscheduled visits: Platelet counts: <100,000 cells/mm^3 or <100 GI/L or reduction from baseline by at least 50%; Hemoglobin: decrease of at least 2 g/dL from baseline or at least Grade 2 (DAIDS); Neutrophil count: Treatment-emergent reduction to at least Grade 2 (DAIDS) (Refer to Section 8.3.6.3.1).

- In case any of the above criteria are met, a confirmatory visit should be scheduled as soon as possible, preferably within 7 days of the receipt of the initial results. Confirmation of the results will trigger weekly or biweekly (every other week) unscheduled visits until improvement or stabilization of the respective parameter(s). Stabilization is defined as no further significant reduction over 2 consecutive visits.
- k. Biochemistry samples should be taken after fasting for at least 10 hours for measurement of phosphate, calcium, creatinine, and lipids. Participants should bring their NA with them to each visit and have that day's intake at the site with food (as applicable), after the sample was taken.
  - l. Creatinine clearance (eGFR calculated by the CKD-EPI formula) will be assessed.
  - m. Refer to Section 8.3.6.1 for management of treatment-emergent ALT/AST elevations.
  - n. Liver function tests only.
  - o. Urinalysis by dipstick: specific gravity, pH, glucose, protein, blood, ketones, bilirubin, urobilinogen, nitrite, leukocyte esterase, and microscopic analysis if needed. The dipstick reading should be done as soon as possible and in accordance with the manufacturer's recommendation. In case of a positive dipstick result, a urine sample will be set aside for additional examination of the positive parameter (eg, quantification as applicable).
  - p. A urinalysis and urine chemistry sample will be taken at FU Week 4 and FU Week 48. In case of abnormalities at FU Week 4, the tests should be repeated at the following visits (from FU Week 8 to FU Week 40).
  - q. Urine chemistry sample (quantitative measurement): creatinine, sodium, phosphate, glucose, protein, and albumin.
  - r. Additional samples may be collected for AFP testing in case of ALT flares.
  - s. Urine pregnancy tests should be done at least every 4 weeks, preferably during a scheduled site visit. Pregnancy tests for at-home use will be provided to the participants from Follow-up Week 24 onwards to allow 4-weekly urine pregnancy testing in between scheduled site visits. If positive, the participant should contact the site immediately.
  - t. Only applicable to participants who are enrolled at a site with access to a Fibroscan device.
  - u. HBcrAg and HBV RNA samples may be batched, and only selected samples may be tested at the sponsor's request. Samples can be used for assessment of other serologic/virologic markers of HBV.
  - v. Exploratory serology samples may be analyzed at the sponsor's discretion. Samples may be used to assess virologic or serologic markers of HBV.
  - w. These samples are optional and will only be collected from participants who consent separately to this component of the study.
  - x. A separate visit may be scheduled for FNA biopsies and blood sample collections for safety labs required prior to FNA biopsy procedures. Participants may stay overnight at the study site after the FNA biopsy procedures at the investigator's discretion. Prior to each FNA biopsy, a recent ( $\leq 2$  weeks) coagulation and hematology panel are required, to ensure normal platelet count and normal coagulation parameters.
  - y. During the follow-up period, whole blood samples for RO assay will be taken at any time during the visit.
  - z. PBMC samples will be collected at selected sites only. Additional PBMC samples may be taken in case of ALT flares, upon discussion with the sponsor, and may require an unscheduled visit. If a PBMC sample has been taken within the last 4 weeks prior to the unscheduled visit, no new PBMC sample is to be collected.
  - aa. Adverse events and concomitant medications will be monitored from the time a signed and dated ISA ICF is obtained until completion of the participant's last ISA-related procedure.
  - bb. Autoantibodies tests include antinuclear antibodies; anti-smooth muscle antibodies; anti-mitochondrial antibodies; anti-thyroid peroxidase antibodies; anti-neutrophil cytoplasmic antibodies; and rheumatoid factor.
  - cc. Optional FNA collection at follow-up Week 48 should be confirmed ahead of the visit with the Sponsor.

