## 5.6.3.2. Renal Safety

Renal safety parameters include the urine creatinine, serum creatinine, urine glucose, total urine protein, total urine albumin, urine protein to creatinine ratio (UPCR), urine albumin to creatinine ratio (UACR), retinol binding protein (RBP), beta-2-microglobulin, RBP to creatinine ratio, beta-2-microglobulin to creatinine ratio, urine fractional excretion of phosphate (FEPO4), Cystatin C, eGFR based on Creatinine (eGFRcr), eGFR based on Cystatin C (eGFRcys).

Descriptive statistics (n, mean, SD, SE, minimum, median, and maximum) will be calculated for each parameter for observed values and changes from baseline at each scheduled time point by intervention arm and analysis phase.

Plots of mean (+/- SE) values and changes from baseline over time for the renal safety parameters will be presented.

A confirmed eGFRcr Grade  $\geq$ 3 is defined as a Grade 3 or higher at 2 consecutive post-baseline measurements or an abnormality observed at 1 measurement followed by study drug discontinuation.

A listing including all renal safety parameters for participants with at least one treatment-emergent eGFRcr Grade 3 or higher will be generated. Another listing will be generated with renal safety parameters for participants who had a confirmed eGFRcr Grade 3 or higher.

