## 5.6.3.2.2. Proximal Renal Tubular Function

#### Proteinuria by Quantitative Assessment

Total urine protein, total urine albumin, UPCR and UACR will be summarized by intervention arm and visit using descriptive statistics.

The number and proportion of participants with UACR and UPCR results in the following categories over time will be tabulated:

- UACR:  $< 30, \ge 30$  to 300, >300 mg/g
- UPCR:  $< 200 \text{ mg/g versus} \ge 200 \text{ mg/g}$

Median (Q1, Q3) percent change from baseline over time will be plotted by intervention arm.

The evolution over time of total urine protein and total urine albumin will also be presented.

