### Proteinuria by Urinalysis (Dipstick)

Treatment-emergent proteinuria by urinalysis (dipstick) over time will be summarized by intervention arm. Cross-tabulation of grades overtime versus baseline will also be presented.

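### Follow-up urine results from FU Week 8 to FU Week 40 come only from participants flagged at FU Week 4, yet the SAP summarises and plots them over time as if everyone were sampled

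*Protocol*

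**What the plan says.** Protocol 1.3.2 (Schedule of Activities, Follow-up Phase), footnote p: "A urinalysis and urine chemistry sample will be taken at FU Week 4 and FU Week 48". It continues: "In case of abnormalities at FU Week 4, the tests should be repeated at the following visits", meaning FU Week 8 to FU Week 40. In the table those seven visits carry the bracketed mark that the key explains as optional or conditional. The footnote does not say which analyte must be abnormal, or by how much.

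The SAP sets these outputs for the same tests:

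- SAP 5.6.3.2, Renal Safety: descriptive statistics for "each parameter for observed values and changes from baseline at each scheduled time point", and "Plots of mean (+/- SE) values and changes from baseline over time for the renal safety parameters will be presented".
- SAP 5.6.3.2.2, quantitative proteinuria: "The number and proportion of participants with UACR and UPCR results in the following categories over time will be tabulated". Also: "Median (Q1, Q3) percent change from baseline over time will be plotted by intervention arm".
- SAP 5.6.3.2.2, dipstick: "Treatment-emergent proteinuria by urinalysis (dipstick) over time will be summarized by intervention arm".
- SAP 5.6.3.1 adds descriptive statistics and graphs for urinalysis at scheduled time points.

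Table 3 of the SAP (Visit Windows) lists FU Week 8 to FU Week 40 as ordinary analysis time points. SAP 5.6 says only that categorical safety variables get counts and percentages; it does not name the denominator.

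**The concern.** Whether a participant has a urine result at FU Week 8 to FU Week 40 depends on that participant's urine result at FU Week 4. A by-visit line or table that runs through those visits changes population twice: from everyone at FU Week 4 to a flagged subset, then back to everyone at FU Week 48. A reader would take the shape of that line as a time course of renal findings after treatment. With 18 and 19 participants per arm, a handful of flagged people would fix each by-arm point, and the arm with more flags at FU Week 4 would supply more of the data.

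Renal findings matter here. Protocol 2.2.3.2 names the kidney as the one target organ of toxicity that JNJ-3989 shares with tenofovir disoproxil and TAF, and NA treatment continues through follow-up.

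**Working it through.** The documents give no figure to reproduce on this point. The check sets the schedule against the SAP outputs, then works out what conditional sampling does to a percentage.

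**Step 1: who is sampled.** In the intervention period urine is scheduled for everyone at Weeks 0, 2, 4, 8, 12, 16, 20 and 24, which is 8 of 10 visits. In follow-up it is scheduled for everyone at FU Weeks 4 and 48, which is 2 of 9. The other seven (FU Weeks 8, 12, 16, 20, 24, 32 and 40) are conditional.

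**Step 2: which outputs are affected.**

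- Dipstick proteinuria, urine protein, urine albumin, UPCR and UACR need urine only, so all seven visits are affected.
- FEPO4 also needs serum creatinine and serum phosphate (SAP 5.6.3.2.2). Footnote n of protocol 1.3.2 limits blood chemistry at FU Weeks 8, 16 and 20 to liver function tests. Scheduled samples can therefore give FEPO4 at 7 − 3 = 4 conditional visits: FU Weeks 12, 24, 32 and 40.
- Retinol binding protein and beta-2-microglobulin have no row in the follow-up schedule, so they are not affected.

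**Step 3: means, medians and changes from baseline.** A participant who was not tested has no value, and the SAP gives no imputation for one. These displays rest on the flagged subset however the percentages are defined.

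**Step 4: percentages.** Let

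- a = share with any urine abnormality at FU Week 4 (the trigger)
- q = share with proteinuria at FU Week 4
- s = probability that proteinuria persists to FU Week 8
- i = probability of new proteinuria at FU Week 8, taken as equal in flagged and unflagged participants

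The documents give none of these; all are assumptions. Then

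- true rate R = qs + (1 − q)i
- rate among those tested T = [qs + (a − q)i] / a
- rate over the full set F = qs + (a − q)i

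Subtracting, T − R = q(s − i)(1/a − 1), which is positive whenever s > i and a < 1. Likewise R − F = (1 − a)i, which is never negative. So under this model the tested denominator overstates and the full-set denominator understates.

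For q = 15%, s = 50%, i = 5%: R = 0.15 × 0.50 + 0.85 × 0.05 = 11.75%. With a = 30%, T = (0.075 + 0.15 × 0.05) / 0.30 = 27.5% and F = 8.25%. The other rows follow in the same way, with the number tested equal to 37 × a.

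| q | a | s | i | Tested (about) | True R | T (tested) | F (full set) |
|---|---|---|---|---|---|---|---|
| 15% | 15% | 50% | 5% | 6 | 11.75% | 50.0% | 7.5% |
| 15% | 30% | 50% | 5% | 11 | 11.75% | 27.5% | 8.25% |
| 15% | 50% | 50% | 5% | 19 | 11.75% | 18.5% | 9.25% |
| 15% | 15% | 80% | 5% | 6 | 16.25% | 80.0% | 12.0% |
| 15% | 50% | 80% | 5% | 19 | 16.25% | 27.5% | 13.75% |
| 15% | 50% | 30% | 2% | 19 | 6.2% | 10.4% | 5.2% |
| 30% | 60% | 50% | 5% | 22 | 18.5% | 27.5% | 16.5% |

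Compare T with q, the rate shown at FU Week 4. It is higher in the first five rows and lower in the last two. F is below q in every row.

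**The case against.** The strongest case on the other side is that this is a small reporting matter, and much of that case stands.

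- **No guaranteed jump.** A reader might infer that proteinuria must rise at FU Week 8 by construction. The documents do not support that. A rise needs a tested-at-visit denominator, which the SAP does not state, and enough persistence. The trigger is any abnormality among ten dipstick parameters and six urine chemistry analytes, so people flagged for ketones or leukocyte esterase, say, dilute the enrichment. The last two rows of the table show no rise, and a full-set denominator shows a fall.
- **Not the tubular markers at FU Week 8.** A reader might extend the point to tubular function generally. Step 2 rules that out. Subclinical tubulopathy is also defined per participant from confirmed abnormalities, not as a visit rate.
- **Not the renal adverse event of special interest.** Renal complications are identified from MedDRA preferred terms (SAP 5.6.2 and Appendix 8), not from these tables. Worst-grade summaries are per participant per phase and show no visit-wise artefact. Creatinine-based eGFR is scheduled in everyone at six follow-up visits (FU Weeks 4, 12, 24, 32, 40 and 48), which gives an unselected renal series. No hypothesis test uses the urine tables.
- **The drop in numbers would show.** The renal descriptive statistics include n, so a careful reader could see it.

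It could also be argued that a conditional visit is not a scheduled time point. The SAP does not say so: Table 3 lists these visits like any other, and the UACR, UPCR and dipstick outputs are simply over time. Elsewhere the SAP does set such limits: seroconversion is assessed only where anti-HBs is available, and liver stiffness is analysed only at Fibroscan sites. Reporting n shows how many were tested, but not that they were chosen on the result being plotted.

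**Conclusion.** The point holds as a minor reporting bias. Followed as written, the SAP produces means, medians, changes from baseline and proportions at FU Week 8 to FU Week 40 from a sample selected on the FU Week 4 urine result. They are not comparable with FU Week 4 or FU Week 48. This covers dipstick and quantitative proteinuria and albuminuria at all seven visits, and FEPO4 at four.

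The selection itself follows directly from footnote p. The size does not: it depends on how broad the trigger is, how persistent the findings are, and which denominator is used. The table is an illustration and not an estimate for this trial. It also assumes that only flagged participants are sampled at those visits, although unscheduled samples remain possible. The direction for percentages (too high among those tested, too low over the full set) holds under the stated model when persistence exceeds new onset. The primary efficacy analysis is untouched.

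**What to change.** In SAP 5.6.3.1, 5.6.3.2 and 5.6.3.2.2:

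1. Limit by-visit follow-up summaries, proportions and plots of urinalysis and urine chemistry results, including FEPO4, to FU Week 4 and FU Week 48.
2. State the denominator for percentages and show the number tested at each visit and in each arm.
3. Report FU Week 8 to FU Week 40 results separately, as a listing or as resolution among participants flagged at FU Week 4.

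The cost is SAP wording and a visit filter. No protocol change or extra sampling is needed, and no result is discarded. The small downside is fewer points on descriptive follow-up plots. The SAP's version history shows that Amendment 2 was written after the primary analysis, so the change would apply to the final analysis outputs.
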